16.1.1 INTENSITY

Intensity is classed as mild/ moderate/ severe. If a participant reports an AE more than once within a SOC/ PT, the AE with the worst-case intensity will be used in the corresponding intensity summaries. In the cases of missing intensity for an AE refer to Section 7.3.2.2.1.

16.1.2 RELATIONSHIP TO FABRAZYME

Relationship, as indicated by the Investigator, is classed as "related", "not related" and "not applicable". If a participant reports the same AE more than once within that SOC/ PT, the AE with the worst-case relationship to study medication will be used in the corresponding relationship summaries. In the cases of missing relationship for an AE refer to Section 7.3.2.2.2.

16.1.3 SERIOUS ADVERSE EVENTS

Serious adverse events (SAEs) are those events recorded where the Serious Event question is marked as Y on the Adverse Events page of the eCRF.

16.1.4 ADVERSE EVENTS LEADING TO DOSE MODIFICATION OR INTERRUPTION (INCLUDING DOSE REDUCED, DRUG INTERRUPTED, INFUSION RATE DECREASED)

TEAEs leading to dose modification or interruption of study medication will be identified where action taken with Fabrazyme is either Dose Reduced, Drug Interrupted, or Infusion Rate Decreased on the eCRF Adverse Events page.

Document: \\ieedc-

 $vnasc 01\BIOS data \Sanofi\Fabrazyme \IAB16602\Biostatistics \Documentation \SAP\SAP\Sanofi\Final \BIOS data \Sanofi\Fabrazyme \BIOS data \Sanofi\Fabrazyme \BIOS data \Sanofi\Fabrazyme \BIOS data \Sanofi\Fabrazyme \BIOS data \BIOS data \Sanofi\Fabrazyme \BIOS data \BIOS da$

Version\lps17726-16-1-9-sap.docx

Author: Version Number: Final V1.0

Version Date: 22Oct2024

Template No.: CS_TP_BS016 Revision 7 Reference: CS_WI_BS005

Effective Date: 01Nov2021

PROTOCOL LPS17726

Analysis Plan Template

Page 54 of 65

16.1.5 ADVERSE EVENTS LEADING TO PERMANENT TREATMENT WITHDRAWAL

TEAEs leading to permanent treatment withdrawal of study medication will be identified where action taken with Fabrazyme is Drug Withdrawal on the eCRF Adverse Events page.

16.1.6 ADVERSE EVENTS LEADING TO DEATH

TEAEs leading to death are those events for which the outcomes are recorded as Fatal on the Adverse Events page of the eCRF.

16.1.7 ADVERSE EVENTS OF SPECIAL INTEREST

16.1.7.1 Infusion Associated Reaction

In this study, IAR is defined as AEs the Investigator considers related to Fabrazyme infusion, occurring on same day as infusion and only after infusion has begun. Each individual AE occurrence will be considered separate when analyzing Adverse Events.

IARs are events recorded as Adverse Event of Special Interest (Infusion Associated Reaction) on the Adverse Events page of the eCRF.

16.1.7.2 ANAPHYLAXIS

See Protocol Section 8.5.6 for details.

Anaphylaxis are events recorded as Adverse Events of Special Interest (Anaphylaxis) on the Adverse Events page of the eCRF.

16.1.8 ANALYSIS OF ADVERSE EVENTS

Events with missing start/end dates and/or time will be handled according to the rules in Appendix 20.1 - 'Algorithm for Treatment Emergent Adverse Events'.

An overall summary table of all TEAEs will be provided for cohorts 1-4 pooled for the SAF

Document: \\ieedc

 $vnasc01\\BIOS data\\Sanofi\\Fabrazyme\\IAB16602\\Biostatistics\\Documentation\\SAP\\SAP\\Sanofi\\Finally and the properties of t$

[figure not shown]
Version\lps17726-16-1-9-sap.docx

Author: Version Number: Final V1.0

Version Date: 22Oct2024

Template No.: CS_TP_BS016 Revision 7 Reference: CS_WI_BS005

Effective Date: 01Nov2021

Page 55 of 65

analysis set and will provide the number and percentage of occurrences along with the total number of events for the following:

For all TEAEs:

- Participants with any TEAE
- Participants with any Severe TEAE
- Participants with any Treatment-Emergent SAE
- Participants with any TEAE leading to Death
- Participants with any TEAE leading to Permanent Discontinuation of Fabrazyme
- Participants with any Treatment-Emergent AESIs: IARs
- Participants with any Treatment-Emergent AESIs: Anaphylaxis
- Participants with any Treatment-Related TEAEs

The AE summaries provided on Table D will be generated with number and percentage of participants experiencing at least one event for the SAF analysis set. Additionally, AE listings in Table E will be provided by cohort for the SAF analysis set.

When evaluating the number of events for participants, multiple occurrences of the same event for the same participant (ie, same SOC and PT) will be as individual events in summary tables. Counts of all AE occurrences will be included in summary tables. All AE occurrences for each participant will be presented in listings.

Table D - Summary Analyses of adverse events

Type of AE	MedDRA levels	
All TEAEs	Primary System Organ Class and Preferred Term	
TEAEs by Maximal Intensity	Primary System Organ Class and Preferred Term	
TEAEs by Worst Relationship to Fabrazyme	Primary System Organ Class and Preferred Term	
Treatment Emergent SAEs	Primary System Organ Class and Preferred Term	
Treatment Emergent SAEs by Worst Relationship to Fabrazyme	Primary System Organ Class and Preferred Term	
TEAEs of Special Interest (IAR)	Primary System Organ Class and Preferred Term	

Document: \\ieedc-

 $vnasc01\\BIOS data\\Sanofi\\Fabrazyme\\IAB16602\\Biostatistics\\Documentation\\SAP\\SAP\\Sanofi\\Finally and the properties of t$

[figure not shown]
Version\lps17726-16-1-9-sap.docx

Author: Version Number: Final V1.0

Version Date: 22Oct2024

Template No.: CS_TP_BS016 Revision 7 Reference: CS_WI_BS005

Effective Date: 01Nov2021

Page 56 of 65

Type of AE	MedDRA levels
All TEAEs	Primary System Organ Class and Preferred Term
TEAEs of Special Interest (Anaphylaxis)	Primary System Organ Class and Preferred Term
TEAE leading to Permanent Full Discontinuation of Study Treatment	Primary System Organ Class and Preferred Term
Pre-treatment Adverse Events	Primary System Organ Class and Preferred Term
Post-treatment Adverse Events	Primary System Organ Class and Preferred Term

Table E - Listings of Adverse Events

Type of AE
All TEAEs
Treatment Emergent Serious Adverse Events (SAEs)
Pre-Treatment Adverse Events
Post-Treatment Adverse Events

16.2 DEATH DETAILS

If any participants die during the study as recorded on the 'death details' page of the eCRF, information available relating to whether an autopsy was performed, the date/time of death along with the primary and secondary cause will be presented in a data listing by cohort for the SAF population.

16.3 LABORATORY EVALUATIONS

Standard clinical and laboratory procedures will be utilized in this study. All clinical and laboratory procedures in this study are standard and generally accepted.

Levels of Lyso-GL3 and ADA will be assessed in the plasma by a central laboratory using standardized and validated methods in addition to applicable calibrated equipment.

Document: \\ieedc

 $vnasc01\\BIOSdata\\Sanofi\\Fabrazyme\\IAB16602\\Biostatistics\\Documentation\\SAP\\Sanofi\\Finally and the property of the property o$

Version\lps17726-16-1-9-sap.docx

Author: Version Number: Final V1.0

Version Date: 22Oct2024

Template No.: CS_TP_BS016 Revision 7 Reference: CS_WI_BS005

Effective Date: 01Nov2021

PROTOCOL LPS17726

Analysis Plan Template

Page 57 of 65

There are no clinical safety laboratory tests planned for this study.

During the study, laboratory exams may be requested at the Investigator's discretion according to the individual needs of each participant.

All laboratory tests with values considered clinically significantly abnormal during participation in the study should be repeated until the values return to normal or baseline or are no longer considered clinically significant by the Investigator or medical monitor. If laboratory values from non-protocol-specified laboratory tests performed at the institution's local laboratory require a change in participant management or are considered clinically significant by the Investigator (eg, SAE or AE or dose modification), then the results must be recorded. If clinically significant values do not return to normal/baseline within a period of time judged reasonable by the Investigator, the etiology should be identified, and the Sponsor notified.

16.4 VITAL SIGNS AND WEIGHT

16.4.1 VITAL SIGNS

Vital Signs data at screening is captured in the Vital Sign eCRF page. Vital Signs data captured at each visit post-screening is captured in the Vital Signs (Timepoint) eCRF pages. Body temperature, heart rate, respiratory rate, and blood pressure will be assessed before and 1 hour after each infusion.

16.4.2 WEIGHT

Weight (kg) will be treated as a vital sign. Weight (kg) data at screening is captured in the Vital Sign eCRF page. Weight (kg) data captured at each visit post-screening is captured in the Vital Signs (Timepoint) eCRF pages.

The amount of Fabrazyme to be administered is dependent on the participant's weight. Before each infusion, the participant must be weighed. If weighing is not possible before each infusion preparation, the site may use the participant's weight obtained for the previous infusion, within 1 month of the date of the infusion.

Document: \\ieedc

Author:

vnasc01\BIOSdata\Sanofi\Fabrazyme\IAB16602\Biostatistics\Documentation\SAP\SAP\Sanofi\Final

[figure not shown]
Version\lps17726-16-1-9-sap.docx

Version Number: Final V1.0

Version Date: 22Oct2024

Template No.: CS_TP_BS016 Revision 7 Reference: CS_WI_BS005

Effective Date: 01Nov2021

PROTOCOL LPS17726

Analysis Plan Template

Page 58 of 65

For analysis only observed weights recorded at the visit as per windowing conventions, see Section 6.6.2, will be presented on outputs. If no record is observed within the window then the value will be considered missing for by visit summaries and presented as missing on listings.

16.4.3 DERIVATIONS

For the below "Visit X" corresponds to post-baseline visits for all X. For quantitative measurements:

- Change from baseline at visit X = Value at Visit X pre-dose Baseline Value
- Change from pre-to post-dose each visit at visit X = Test Value at Visit X post-dose
 Test Value at Visit X pre-dose

To convert temperature (F) to temperature (°C):

• Temperature (°C) = [Temperature (F) – 32] x (5/9)

16.4.4 VITAL SIGNS AND WEIGHT POTENTIALLY CLINICALLY SIGNIFICANT ABNORMALITY CRITERIA

Potentially clinically significant abnormality (PCSA) quantitative Vital Signs and weight measurements will be identified in accordance with the following predefined markedly abnormal criteria:

Age Group: ≥18 years old

Variable	Unit	Low	High
SBP	mmHg	≤90 AND	≥180 AND
		change from baseline \leq -20 change from baseline \geq 20	
DBP	mmHg	≤50 AND	≥105 AND
		change from baseline ≤-15 change from baseline ≥15	
Heart rate	Bpm	≤50 AND ≥120 AND	
		change from baseline ≤-15	change from baseline ≥15

Document: \\ieedc-

 $vnasc01\BIOSdata\Sanofi\Final\Version\lps17726-16-1-9-sap.docx$

Author: Version Number: Final V1.0

[figure not shown]
Reference: CS_WI_BS005

22Oct2024

Version Date:

Template No.: CS_TP_BS016 Revision 7 Referen

Effective Date: 01Nov2021

Page 59 of 65

Variable	Unit	Low	High
Body	°C	NA	≥38.3 AND
temperature			change from baseline ≥1.1
Weight	Kg	percentage change from	percentage change from
		baseline ≤-7.0 %	baseline ≥7.0 %

Age Group: 6 to <12 Years Old

Variable	Unit	Low	High
SBP	mmHg	≤80 AND	≥108 AND
		change from baseline ≤-20	change from baseline ≥20
DBP	mmHg	≤48 AND	≥72 AND
		change from baseline \leq -10 change from baseline \geq 10	
Heart rate	Bpm	≤50 AND	≥120 AND
		change from baseline \leq -20 change from baseline \geq 20	
Body	°C	NA	≥38
temperature			
Weight	Kg	percentage change from	
		baseline ≤-5.0 %	

Age Group: 12 to 18 years old

Variable	Unit	Low	High
SBP	mmHg	≤90 AND	≥119 AND
		change from baseline ≤-20	change from baseline ≥20
DBP	mmHg	≤54 AND	≥78 AND
		change from baseline \leq -10 change from baseline \geq 10	
Heart rate	Bpm	≤50 AND	≥120 AND
		change from baseline \leq -20 change from baseline \geq 20	
Body	°C	NA	≥38
temperature			
Weight	Kg	percentage change from	
		baseline ≤-5.0 %	

Document: \\ieedc-

 $vnasc 01 \\BIOS data \\Sanofi \\Fabrazyme \\IAB16602 \\Biostatistics \\Documentation \\SAP \\Sanofi \\Finally \\Sanofi \\Finally \\Finally$

Version\lps17726-16-1-9-sap.docx

Author: Version Number: Final V1.0

Version Date: 22Oct2024

Template No.: CS_TP_BS016 Revision 7 Reference: CS_WI_BS005

Effective Date: 01Nov2021

PROTOCOL LPS17726

Analysis Plan Template

Page 60 of 65

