5.1 Inclusion Criteria

Participants are eligible to be included in the study only if all the following criteria apply:

- 1. Participants with confirmed diagnosis of FD who are ≥2 and ≤65 years of age at the time of signing the informed consent form (ICF) or assent, if applicable.
 - a. Cohort 1: female participants with body weight ≥30 kg who have been treated with Fabrazyme for at least 3 months without IARs during the most recent 3 infusions.
 - b. Cohort 2: non-classic male participants with body weight ≥30 kg who have been treated with Fabrazyme for at least 3 months without IARs during the most recent 3 infusions.
 - c. Cohort 3: classic male participants with body weight ≥30 kg who have been treated with Fabrazyme for at least 3 months without IARs during the most recent 3 infusions.
 - d. Cohort 4: participants with body weight <30 kg who have been treated with Fabrazyme for at least 3 months without IARs during the most recent 3 infusions.

Note: Classic FD is defined by α GAL level in dried blood spot or leukocyte below 3% of normal value.

2. Women of childbearing potential must use a highly effective method of contraception through the study (refer to Appendix 4 in Section 10.4).

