3 STUDY DESIGN

3.1 GENERAL DESCRIPTION

This is a Phase 4, prospective, open label, single arm, interventional study, to be conducted in the US, to evaluate the safety and tolerability of Fabrazyme at approved dose of 1 mg/kg and increased infusion rate and reduced infusion volume.

Up to 14 participants with Fabry disease will be enrolled to study intervention in 4 cohorts:

- Cohort 1: 3 Fabrazyme experienced female participants (body weight ≥30 kg)
- Cohort 2: 3 Fabrazyme experienced non-classic male participants (body weight ≥30 kg)
- Cohort 3: 4 Fabrazyme experienced classic male participants (body weight ≥30 kg)
- Cohort 4: 4 Fabrazyme experienced participants (body weight <30 kg)

Classic FD is defined by α GAL level in dried blood spot or leukocyte below 3% of normal value and all others are considered as non-classic disease.

Screening will be performed up to 4 weeks prior to the first dose of study intervention. Enrolled participants will receive treatment for up to 16 weeks and have an End-of-Study Visit 28 weeks after the start of the treatment. Participants will undergo visits and study procedures as shown in Schedule of Activities (SoA) presented in Section 1.3 of the protocol. A flow chat illustrating the key components of the study is provided in Figure 1.

Document: \\ieedc-

 $vnasc01\BIOS data\Sanofi\Fabrazyme\IAB16602\Biostatistics\Documentation\SAP\SAP\Sanofi\Final$

Version\lps17726-16-1-9-sap.docx

Author: Version Number: Final V1.0

Version Date: 22Oct2024

[figure not shown]
Template No.: CS_TP_BS016 Revision 7 Reference: CS_WI_BS005

Effective Date: 01Nov2021

Page 18 of 65

Figure 1: Study Schema

Abbreviations: ADA = anti-drug antibody (ie, anti-agalsidase beta IgG antibody); AE = adverse event; AESI = adverse event of special interest; EOS = end-of-study; EOT = end-of-treatment; IAR = infusion associated reaction; lyso-GL3 = globotriaosylsphingosine; Q2W = every 2 weeks; SAE = serious adverse events; V = visit; W = week.

- a. V1 and V2 can take place on the same day. The number of visits during the Study Intervention Period (ie, Visits 2 to 10) may differ between participants, as those having a second IARs will discontinue the study intervention, and those who successfully reaches the shortest infusion duration planned for the cohort to which they belong will be considered as treatment completers. All participants will stay in the study for the follow-up visits at Week 12 and Week 28.

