16.4.5 ANALYSIS OF VITAL SIGNS AND WEIGHT

Vital signs data will be analyzed for the SAF analysis set for the following parameters:

- Systolic blood pressure (mmHg)
- Diastolic blood pressure (mmHg)
- Heart rate (bpm)
- Respiratory rate (bpm)
- Body temperature (°C)
- Weight (kg)

The following summaries based on observed data will be provided for the study treatment period:

- Values at each visit.
- Change from baseline at each visit for pre-dose vital signs.
- Change from pre-dose to post-dose at each visit (for all parameters except weight [kg])
- Incidence of predefined markedly abnormal criteria by age group and parameter.

Participants who have markedly abnormal values in both directions (abnormally high and abnormally low) during the study treatment period for the same parameter will be included in both high and low counts for that parameter.

Corresponding listings will also be provided detailing the above summaries, including the date and time of assessment and reasons if known as to why a scheduled assessment was not conducted. Listings will also include what abnormality is satisfied at each visit pre/post infusion.

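### The vital-sign abnormality criteria have no band for ages 2 to 5 and place age 18 in two bands with conflicting limits

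*SAP*

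**What the plan says.** Protocol Section 5.1 admits participants who are "≥2 and ≤65 years of age at the time of signing the informed consent form". Cohort 4 takes up to 4 of the 14 participants and is defined by body weight below 30 kg, not by age.

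SAP Section 16.4.4 gives the PCSA limits in three tables, headed "Age Group: ≥18 years old", "Age Group: 6 to <12 Years Old" and "Age Group: 12 to 18 years old". Section 16.4.5 then plans, among the vital-sign summaries for the study treatment period, "Incidence of predefined markedly abnormal criteria by age group and parameter". It also plans listings that show which abnormality is met at each visit, before and after infusion.

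SAP Section 10 groups age differently for the baseline tables: 2 to 10, 11 to 17, and 18 to 65 years. That scheme includes the youngest children and treats 18 as adult only. Tables 3 and 4 in Protocol Section 6.1 have premedication entries that start at age 2, so participants of that age are expected.

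**The concern.** The three PCSA tables do not cover the eligible age range once each. The youngest eligible participants have no rule, and one age has two rules with no statement of which prevails.

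Protocol Section 9.3.5 names vital signs as a safety endpoint, and Protocol Section 8.4.2 plans no clinical safety laboratory tests. Scheduled vital signs are therefore a large part of the objective safety data. The PCSA incidence is also the only vital-sign summary that SAP Section 16.4.5 splits by age. Section 7 pools cohorts 1 to 4 for summaries, and Section 7.5 rules out subgroup analyses.

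If the rules are followed as written, that output is incomplete for ages 2 to 5 and can contradict itself at age 18. The gap would then be settled during programming, after data from an open-label trial have been seen.

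**Working it through.** The documents give no figure to reproduce here. The check compares the age bands with eligibility.

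**1. Coverage**

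Inputs: ages 2 to 65 (Protocol Section 5.1) and the bands 6 to <12, 12 to 18 and ≥18 (SAP Section 16.4.4). There are 65 − 2 + 1 = 64 whole-year ages.

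| Age (years) | PCSA bands that contain it | Number of ages |
|---|---|---|
| 2, 3, 4, 5 | none | 4 |
| 6 to 11 | 6 to <12 | 6 |
| 12 to 17 | 12 to 18 | 6 |
| 18 | 12 to 18, and ≥18 | 1 |
| 19 to 65 | ≥18 | 47 |

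The rows sum to 4 + 6 + 6 + 1 + 47 = 64. Four ages have no band and one has two.

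**2. Whether the overlap at 18 changes a result**

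| Illustrative finding at age 18 | 12 to 18 table | ≥18 table |
|---|---|---|
| SBP 125 mmHg, rise of 20 | limit ≥119 and rise ≥20: abnormal | limit ≥180 and rise ≥20: normal |
| Heart rate 50 bpm, fall of 16 | limit ≤50 and fall ≥20: normal | limit ≤50 and fall ≥15: abnormal |

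The tables disagree in both directions, so neither is uniformly the stricter. Some entries do agree: the low systolic criterion is the same in both (≤90 with a fall of at least 20), and the heart-rate cut-offs match apart from the required change.

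**3. How many participants the gap could affect**

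The documents give no ages. Assume that every participant aged 2 to 5 weighs under 30 kg and so belongs to cohort 4. The number is then 0 to 4 of 14:

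- lower bound 0/14 = 0%
- upper bound 4/14 = 28.6%

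**4. Why the denominator matters**

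SAP Section 7 allows a percentage to be based on the whole analysis set or on participants with assessments available. It does not say which applies to PCSA incidence. Suppose 4 of 14 treated participants have no applicable criteria and one other participant is flagged. Pooled over ages, the incidence is 1/14 = 7.1% on the whole set and 1/10 = 10.0% on those who could be assessed.

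**5. After the correction**

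With bands 2 to <6, 6 to <12, 12 to <18 and ≥18, each of the 64 ages falls in exactly one band.

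**The case against.** The strongest reply is that little is lost. SAP Section 16.4.5 still summarises values, changes from baseline and pre- to post-dose changes for every treated participant, and the listings show the observed values. The protocol's statistical section commits only to actual values and changes for safety variables, and that commitment is met at ages 2 to 5. Investigators also report hypertension, hypotension, tachycardia and tachypnea as infusion associated reactions using age-appropriate ranges (Protocol Section 8.5.6). The anaphylaxis definition there has its own blood-pressure rule for children under 10, and clinically significant vital signs can be adverse events under Section 10.3.1. None of these routes depends on SAP Section 16.4.4. All of this stands, and it limits the point to the PCSA incidence output and the PCSA flags in listings.

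Age 18 also has an evident intended reading, since SAP Section 10 counts 18 as adult. That is fair, but Section 16.4.4 has no such rule and the printed bounds overlap.

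Several stronger readings are tempting but not supported:

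- **The youngest children would be reported with zero abnormalities, as a clean result.** The output is by age group, so they might simply have no row. The table shells are not in the documents, and nothing says these children would be counted as normal.
- **Abnormal vital signs in these children would go undetected.** The values and the investigator reporting described above remain.
- **29% of the trial is affected.** That is the size of cohort 4, which is defined by weight; it is an upper bound.
- **This falls on the cohort with the least prior data.** The documents do not rank the cohorts in this way, and Protocol Section 2.1 cites tolerability data in boys under 30 kg.
- **The lack of a respiratory-rate criterion is part of the same defect.** Respiratory rate is an analysed parameter with no PCSA row in any table, but nothing in the documents requires a criterion for every parameter. It is still summarised and listed, and the omission is unrelated to the age bands.

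**Conclusion.** The point holds for the age bands. Ages 2, 3, 4 and 5 are eligible but have no PCSA criteria, and age 18 has two sets that can give opposite classifications.

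The gap affects between 0 and 4 of 14 participants, assuming that all participants aged 2 to 5 are in cohort 4. The overlap matters only if an 18-year-old is enrolled. If the trial has neither, the defect has no effect on the results, though the text is still wrong.

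The consequence is an incomplete or ambiguous descriptive safety output. The primary and secondary endpoints and the detection of infusion associated reactions are untouched. The correction should be made, but it does not threaten the trial's conclusions.

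**What to change.** Amend SAP Sections 16.4.4 and 16.4.5 before database lock:

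1. Add a 2 to <6 years band with criteria pre-specified by the sponsor. If no participant of that age was enrolled, say so instead. No limits are proposed here.
2. Change the upper bound of the adolescent band so that it reads 12 to <18. Age 18 then falls only in the adult band, as in SAP Section 10.
3. Show the number of participants assessed in each band and use it as the denominator, so that the absence of a rule is not read as the absence of abnormality.

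The cost is a table edit in the SAP and minor programming. The protocol and data collection do not change.
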